11.6 SAMPLE SIZE JUSTIFICATION

A sample size of 186 subjects in total (BF-200 ALA: 149 subjects and vehicle: 37 subjects) in the FAS at a randomization of 4:1 was estimated to ensure at least 90% power to demonstrate superiority of BF-200 ALA compared to vehicle by means of a Cochran-Mantel-Haenszel Test with baseline number of lesion (1 vs. ≥ 2 lesion) and center as stratification factors on a significance level of 0.1% ($\alpha=0.001$; one-sided).

This estimate was based on the following quantities and assumptions:

- The estimated response rate for sBCCs is based on data previously established during ALA-BCC-CT008 that was conducted in the EU comparing safety and efficacy of BF-200 ALA with Metvix®. This study revealed a complete clinical patient response rate of 91% (FAS) for subjects with sBCC only, treated with BF-200 ALA and a 1-year cumulated recurrence rate of 11% and a 2-year recurrence rate of 18% (FAS) setting identified recurrent patients as well as patient lost to follow-up as recurrent (data on file and (31)).

- With respect to individual sBCC lesions, this study revealed a total lesion response rate for BF-200 ALA of 93% (FAS). The respective lesion recurrence rates after 1 year and 2 years were 8.8% and 16% taking recurrent as well as lost to follow up lesions into account.
- Taking into account a maximum of 18% of patients showing a recurrence (worst case, also lost to follow-up patients are regarded as recurrent) at 2 years follow-up. These may have shown a potentially histologically positive result at the last clinical visit which leads to the estimate of 72.9% of patients who are assumed to be clinically and histologically cleared 12 weeks after the last PDT. We expect a proportion of 10% of patients with a missing histological assessment 12 weeks after the last PDT.
- As no further data on vehicle/placebo treatment in sBCC in combination with PDT are available, historic data were used as a basis for the sample size calculation with respect to vehicle treatment:
 - Published data from the FDA Clinical and Statistical Review presentation (NDA 21-576) on nBCC studies with Metvix® PDT. These revealed a complete clinical and histological subject response to verum ranging from 64% and 73% and to vehicle ranging from 15% to 25% according to Agency Analysis.

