## Table 1: Visit terminology

Notation in protocol	Notation used for TLG presentation
Visit 1, Screening (≤ 4 weeks prior to PDT-1)	Screening
Randomization at Visit 2, PDT-1 (Baseline)	Randomization
Visit 2, PDT-1 (Baseline)	PDT-1
Not applicable	Baseline 
Visit 3, PDT-2 (1-2 weeks post-PDT-1)	PDT-2
Phone call 1 (1 week ± 2 days post-PDT-2)	1 week post-PDT-2
Visit 4 (5 weeks ± 1 week post-PDT-1)	5 weeks post-PDT-1
Visit 5, PDT-3 (12 weeks ± 1 week post-PDT-1)	PDT-3 / 12 weeks post-PDT-1
Visit 6, PDT-4 (1-2 weeks post-PDT-3)	PDT-4
Phone call 2 (1-week ± 2 days post-PDT-4)	1 week post-PDT-4
Visit 7 (5 weeks ± 1 week post-PDT-3)	5 weeks post-PDT-3
Visit 8 (12 weeks ± 1 week post-PDT-3)	12 weeks post-PDT-3
Not applicable	12 weeks after start of the last PDT cycle 

 Baseline is defined as last non-missing value until PDT-1, i.e. non-missing observation on PDT-1 visit or non-missing observation on Screening visit will be used as Baseline value. Non-missing observation on PDT-1 visit will be used as Baseline value if assessment was performed before treatment (before drug application and light treatment). Non-missing observation on Screening visit will be used as Baseline value in following cases:

- if no assessment on PDT-1 visit was performed and non-missing observation on Screening visit is available,
- if assessment on PDT-1 visit was performed after treatment (after drug application and light treatment) and non-missing observation on Screening visit is available,
- if assessment on PDT-1 visit was performed before treatment (before drug application and light treatment) and assessment observation is missing and non-missing observation on Screening visit is available.

If the absolute change from Baseline is calculated for a parameter or Baseline characteristics are presented, this artificial visit will be displayed in the corresponding tables and Baseline value will be indicated in corresponding listings.

 For complete responders, Visit 5 will be used as 12 weeks after the start of the last PDT cycle visit, for non-responders or partial responders, Visit 8 will be used. For analysis reasons, these visits will be combined to the artificial visit "12 weeks after start of the last PDT cycle" and will be displayed in the corresponding tables and used value will be indicated in corresponding listings.

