#### 2.3 Further Secondary Efficacy Variables

The following further secondary efficacy parameters will be analyzed:

- Lesion complete clinical response rate per treatment arm (complete clearance of individual lesions (Main and Additional Target Lesions)) according to clinical assessment only, assessed 12 weeks after the start of the last PDT cycle.
- Main Target Lesion complete response (clinically and histologically cleared) assessed 12 weeks after PDT-1.
- Main Target Lesion clinical response (according to clinical assessment only) assessed 12 weeks after PDT-1.
- Main Target Lesion histological response (according to histological assessment only) assessed 12 weeks after PDT-1.
- Lesion complete clinical response rate per treatment arm (complete clearance of individual lesions (Main and Additional Target Lesions)) according to clinical assessment only, assessed 12 weeks after PDT-1.
- Subject complete clinical response (complete clearance of all Target Lesions according to clinical assessment only) assessed 12 weeks after PDT-1.
- Subject complete response (clinically and histologically cleared Main Target Lesion (see above) and complete clinical remission of all Additional Target Lesions) assessed 12 weeks after PDT-1.
- For all Target Lesions, assessment of esthetic appearance by the investigator 12 weeks after the start of the last PDT cycle, but prior to surgical excision of the Main Target Lesion and any alternative treatment of Additional Target Lesions.
- Subjects' satisfaction regarding esthetic outcome and treatment 12 weeks after the start of the last PDT cycle, but prior to surgical excision of the Main Target Lesion or alternative treatment of Additional Target Lesions at the end of the clinical observation period.

10/29

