## 4.4.3 Analysis of Further Efficacy Variables

All further secondary efficacy variables will be analyzed descriptively and in an exploratory way. All analyses will be performed on the FAS and PPS. All statistical testing procedures will be done exploratory using a significance level of 5% ( $\alpha$ =0.05, two-sided).

Lesion complete clinical response rate per treatment arm (complete clearance of individual lesions (Main and Additional Target Lesions)) according to clinical assessment only, assessed 12 weeks after the start of the last PDT cycle.

The lesion complete clinical response rate is defined as the percentage of completely cleared individual lesions, in relation to the number of lesions at baseline (Visit 2).

The lesion complete clinical response rate per treatment arm 12 weeks after the start of the last PDT cycle will be analyzed descriptively. The absolute number of target lesions at baseline and the absolute and relative frequency of clinically cleared lesions 12 weeks after the start of the last PDT cycle will be tabulated per treatment arm.

As additional analyses, the lesion complete clinical response rate per treatment arm 12 weeks after the last PDT cycle will be analyzed descriptively by location of lesions and baseline size of lesions. Frequencies per subgroup category will be presented.

Main Target Lesion complete response (clinically and histologically cleared) assessed 12 weeks after PDT-1.

Main Target Lesion complete response is defined as response according to clinical and histological assessment.

The Main Target Lesion complete response 12 weeks after PDT-1 will be analyzed using a Cochran-Mantel-Haenszel Test (incl. confidence interval) with baseline number of lesions (1 vs.  $\geq$ 2 lesion(s)) and center as stratification factors.

As additional analyses, the Main Target Lesion complete response 12 weeks after PDT-1 will be analyzed descriptively by location of Main Target Lesion and baseline size of Main Target Lesion. Two-sided exact 95% CI for the difference in response rates will be calculated.

Main Target Lesion clinical response (according to clinical assessment only) assessed 12 weeks after PDT-1.

Main Target Lesion clinical response is defined as response according to clinical assessment only.

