The Main Target Lesion clinical response 12 weeks after PDT-1 will be analyzed using a Cochran-Mantel-Haenszel Test (incl. confidence interval) with baseline number of lesions (1 vs.  $\geq$ 2 lesion(s)) and center as stratification factors.

As additional analyses, the Main Target Lesion clinical response 12 weeks after PDT-1 will be analyzed descriptively by location of lesions and baseline size of Main Target Lesion. Two-sided exact 95% CI for the difference in response rates will be calculated.

Main Target Lesion histological response (according to histological assessment only) assessed 12 weeks after PDT-1.

Main Target Lesion histological response is defined as response according to histological assessment only.

The Main Target Lesion histological response 12 weeks after PDT-1 will be analyzed using a Cochran-Mantel-Haenszel Test (incl. confidence interval) with baseline number of lesions (1 vs.  $\geq$ 2 lesion(s)) and center as stratification factors.

As additional analyses, the Main Target Lesion histological response 12 weeks after PDT-1 will be analyzed descriptively by location of lesions and baseline size of Main Target Lesion. Twosided exact 95% CI for the difference in response rates will be calculated.

Lesion complete clinical response rate per treatment arm (complete clearance of individual lesions (Main and Additional Target Lesions)) according to clinical assessment only, assessed 12 weeks after PDT-1.

The lesion complete clinical response rate per treatment arm is defined as the percentage of individual lesions in the respective treatment arm with complete clearance.

The lesion complete clinical response rate per treatment arm 12 weeks after PDT-1 will be analyzed descriptively. The absolute number of target lesions at baseline and the absolute and relative frequency of clinically cleared lesions 12 weeks after the start of the last PDT cycle will be tabulated per treatment arm.

Subject complete clinical response (complete clearance of all Target Lesions according to clinical assessment only) assessed 12 weeks after PDT-1.

The subject complete clinical response is defined as complete clearance of all target lesions according to clinical assessment only.

The subject complete clinical response 12 weeks after PDT-1 will be analyzed using a Cochran-Mantel-Haenszel Test (incl. confidence interval) with baseline number of lesions (1 vs.  $\geq$ 2 lesion(s)) and center as stratification factors.

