## 4.6 Missing Values

Missing values for the primary and secondary endpoints will be imputed as follows:

For all subjects missing values for the primary and secondary endpoints for the first PDT cycle will be imputed as follows:

- For the analysis of the composite endpoint clinical and histological response of the Main Target Lesion a missing clinical and/or histological lesion assessment of the Main Target Lesion on Visit 5 will be considered as non-response.
- For the analysis of histological response only a missing histological lesion assessment of the Main Target Lesion on Visit 5 will be considered as non-response.
- For the analysis of clinical response only of the Main Target Lesion as well as for the clinical response of Additional Target Lesions a last observation carried forward (LOCF) approach will be used to impute clinical assessments on Visit 5: If the clinical assessment of lesion clearance (yes/no) on week 12 after PDT-1 (i.e. Visit 5) is missing but week 5 after PDT-1 (i.e. Visit 4) assessment is available, missing week 12 after PDT-1 data will be imputed by week 5 after PDT-1 data. If a lesion clearance is not assessed on week 5 after PDT-1 and on week 12 after PDT-1, the lesion will be regarded as non-responder on Visit 5. Lesions with missing clinical assessments on Visit 4 will be regarded as non-responders.

For partial/non-responders at Visit 5 or subjects imputed as partial/non-responders at Visit 5 missing values for the primary and secondary endpoints for the second PDT cycle will be imputed as follows:

- For the analysis of the composite endpoint clinical and histological response of the Main Target Lesion a missing clinical and/or histological lesion assessment of the Main Target Lesion on Visit 8 will be considered as non-response.
- For the analysis of histological response only a missing histological lesion assessment of the Main Target Lesion on Visit 8 will be considered as non-response, if the Main Target Lesion was not already clinically cleared and excised at Visit 5. If the Main Target Lesion was already clinically cleared and excised at Visit 5, the histological lesion assessment of the Main Target Lesion at Visit 5 will be carried forward to Visit 8 following a last observation carried forward (LOCF) approach.

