- For the analysis of clinical response only of the Main Target Lesion as well as for the clinical response of Additional Target Lesions a last observation carried forward (LOCF) approach will be used to impute missing clinical assessments: If the clinical assessment of lesion clearance (yes/no) on week 12 after PDT-3 (i.e. visit 8) is missing but week 5 after PDT-3 (i.e. visit 7) assessment is available, missing week 12 after PDT-3 data will be imputed by week 5 after PDT-3 data. If a lesion clearance is not assessed on week 5 after PDT-3 and on week 12 after PDT-3, the lesion will be regarded as non-responder on Visit 7 and Visit 8.
- For complete responders after cycle 1 who by mistake received a second treatment cycle, evaluations of the 1st cycle will be considered for all efficacy analyses, including the primary analysis.
- No replacement of missing values will be done for the secondary endpoints assessment of esthetic appearance by the investigator and subjects' satisfaction regarding esthetic outcome.

No additional methods on replacement of missing values of efficacy variables will be applied.

As sensitivity analysis for the primary and selected secondary efficacy variables additionally a complete cases analysis will be done.

Missing values of safety variables will not be replaced.

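### The SAP's table instruction for lesion clearance 12 weeks after PDT-1 names the last-cycle time point, so the one-cycle lesion rate is not specified

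*SAP*

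**What the plan says.** Protocol 11.1.2 and SAP 2.3 both list two separate lesion-level clinical clearance rates covering Main and Additional Target Lesions: one 12 weeks after the start of the last PDT cycle, the other 12 weeks after PDT-1.

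SAP 4.4.3 then describes how each is analysed.

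- Last-cycle endpoint. The lead sentence is "The lesion complete clinical response rate per treatment arm 12 weeks after the start of the last PDT cycle will be analyzed descriptively". The table is to show the number of target lesions at baseline and the "relative frequency of clinically cleared lesions 12 weeks after the start of the last PDT cycle will be tabulated per treatment arm".
- PDT-1 endpoint. The heading names PDT-1, and the lead sentence is "The lesion complete clinical response rate per treatment arm 12 weeks after PDT-1 will be analyzed descriptively". The next sentence, the only one that specifies a table, again calls for the "relative frequency of clinically cleared lesions 12 weeks after the start of the last PDT cycle will be tabulated per treatment arm".

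SAP Table 1 assigns 12 weeks post-PDT-1 to Visit 5. Its second footnote builds the last-cycle time point from two visits: complete responders contribute Visit 5, while "for non-responders or partial responders, Visit 8 will be used".

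**The concern.** The PDT-1 endpoint has a heading and a lead sentence for one time point and a table instruction for another. The two time points differ for every subject who goes on to a second cycle. A table programmed from the instruction would combine results after one cycle with results after up to two, and would reproduce the table already specified for the last-cycle endpoint.

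What would be lost is the one-cycle clearance rate that counts each Main and Additional Target Lesion individually. The first cycle is the obligatory part of the regimen, and Additional Target Lesions enter only the secondary efficacy and safety analyses, so this is where their individual one-cycle clearance would be reported. If the table instead carried a PDT-1 title over last-cycle data, readers could take a result after up to two cycles for a one-cycle result.

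**Working it through.** The plan states no figure for this endpoint, so there is none to reproduce. The check is a comparison of text, followed by an illustration of size.

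**Comparison of the two entries in SAP 4.4.3**

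| Element | Last-cycle endpoint | PDT-1 endpoint |
|---|---|---|
| Heading | Last PDT cycle | PDT-1 |
| Lead analysis sentence | Last PDT cycle | PDT-1 |
| Table instruction | Last PDT cycle | Last PDT cycle |
| Lesion count tabulated | Target lesions at baseline | Target lesions at baseline |

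The two table instructions were compared character by character and are identical. With the same numerator, baseline count and arms, they produce the same table.

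**Is the change deliberate?** SAP section 5 lists the departures from the protocol, and this is not among them. The other five response endpoints at 12 weeks after PDT-1 in SAP 4.4.3 (three for the Main Target Lesion, two at subject level) keep PDT-1 in their analysis sentences. The pattern is that of a copied sentence.

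**Does another table fill the gap?** The by-visit clinical frequency tables in SAP 4.4.2 cover the Main Target Lesion or the subject as a whole. The last-cycle lesion table in 4.4.3 is not by visit. No other lesion-level table at Visit 5 appears in the SAP text.

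**Size, if last-cycle data stood under a PDT-1 label**

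Let c be the proportion of lesions cleared at Visit 5 and r the proportion of the remaining lesions cleared on retreatment. If every lesion cleared at Visit 5 still counts as cleared:

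- last-cycle rate = c + (1 − c) × r
- excess over the one-cycle rate = (1 − c) × r

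The documents give neither c nor r. Protocol 11.6 gives a lesion response rate for BF-200 ALA of 93% (FAS) in the earlier European trial. Taking that as the last-cycle rate and assuming c:

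| Assumed c | Excess | Implied r |
|---|---|---|
| 60% | 93 − 60 = 33 points | 0.33 / 0.40 = 0.825 |
| 80% | 93 − 80 = 13 points | 0.13 / 0.20 = 0.65 |
| 90% | 93 − 90 = 3 points | 0.03 / 0.10 = 0.30 |

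Dropping the 93% and varying both inputs, c from 50% to 80% and r from 30% to 70%, gives an excess between 0.20 × 0.30 = 6 points and 0.50 × 0.70 = 35 points. No clinical-only lesion rate for vehicle is given, so no vehicle figure is offered.

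**An offset.** Under SAP 4.6, if a partial responder's lesion is unassessed at both later visits, "the lesion will be regarded as non-responder on Visit 7 and Visit 8". Each 1% of lesions cleared at Visit 5 but lost this way lowers the last-cycle figure by 1 point. Two cases show the range of effects:

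- One lesion, not cleared at Visit 5 and cleared at Visit 8: 0/1 at Visit 5, 1/1 in the literal table.
- Two lesions, the Main Target Lesion cleared and excised at Visit 5 and not assessed afterwards, the other cleared only at Visit 8: 1/2 at Visit 5, 1/2 in the literal table.

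Overstatement is therefore the likely direction, but it is not certain for every subject.

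**The case against.** The intent is easy to infer. The protocol, SAP 2.3, the endpoint's heading and the sentence just before the table instruction all name PDT-1. SAP 4.6 also provides that "a last observation carried forward (LOCF) approach will be used to impute clinical assessments on Visit 5", and this covers Additional Target Lesions. A careful programmer would probably produce the right table, and two identical tables under different titles would be noticed at output review. According to SAP 4.9, Appendix A determines the variables of the standard tables; it was not in the available text and may be correct. The endpoint is exploratory and descriptive. One-cycle clinical response is properly specified for the Main Target Lesion and at subject level for all target lesions, and Visit 5 lesion status is collected for everyone, so the table could be produced later. The point figures rest on assumed cycle-1 rates.

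Most of this stands, and it limits the consequences. Whether a wrong table results depends on Appendix A and on how literally the text is followed. The figures are arithmetic on assumptions, not estimates. What the objection does not remove is the error: the SAP text's only output instruction for a listed endpoint names the wrong time point. That the intent can be guessed does not make the instruction correct.

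**Conclusion.** The concern holds. As written, SAP 4.4.3 specifies the last-cycle lesion table twice and the one-cycle lesion table not at all, against its own heading and lead sentence, SAP 2.3 and Protocol 11.1.2. The gap is confined to the rate that counts individual lesions, including Additional Target Lesions, after one cycle.

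The size of any mislabelling cannot be derived from the documents. The illustration of 3 to 33 points for BF-200 ALA requires that the last-cycle rate equal the earlier trial's 93%, that cycle-1 clearance lie between 60% and 90%, and that lesions cleared at Visit 5 remain counted as cleared. The primary test, the key secondary hierarchy, the significance level and the sample size are unaffected. Confidence is high on the mismatch in the text; whether Appendix A repeats it is unknown. It should be corrected, but it does not threaten the trial's main conclusions.

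**What to change.** In the table instruction under the PDT-1 lesion endpoint in SAP 4.4.3, replace the reference to the start of the last PDT cycle with PDT-1 (Visit 5). Keep the baseline lesion count as denominator and the Visit 5 imputation rule already in SAP 4.6. Check that the table description in Appendix A names the same visit.

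The cost is one phrase and one check. No new data, method or imputation rule is needed.

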## 4.5 Safety Analysis

All safety endpoints will be analyzed descriptively and in an exploratory way. The safety analyses will be performed for the SAF.

AEs will be presented with maximum intensity.

AEs will be coded according to the latest Medical Dictionary for Regulatory Activities (MedDRA) version available at the day of database closure, system organ class (SOC) and preferred term (PT) will be presented. The AE analysis will focus on the TEAEs.

#### Frequency and extent of TEAEs, including SAEs

TEAEs are defined as all AEs with time of onset on or after the time of treatment with randomized IMP within 4 weeks (28 days) after each PDT cycle. If time of onset of AEs is not within 4 weeks (28 days) after each PDT cycle, but is identified to be at least possibly related to IMP or medical device, AEs will be assumed as TEAEs. The reference dates will be calculated as date of last PDT within each PDT cycle + 28, i.e. date of PDT-2 and/or PDT-4, respectively. If PDT-2 and/or PDT-4 are not available, the dates of PDT-1 and/or PDT-3 will be used for calculation of reference dates. These reference dates will be used for assignment of TEAEs. If unclear due to incomplete start time/date of AE or PDT, AEs will be assumed as TEAEs, as far as end time/date of AE is not before first treatment in first PDT cycle. AEs and TEAEs will be summarized and tabulated according to primary system organ class and preferred term displaying the number of events as well as counts and percentages on a subject basis per treatment arm.

[figure not shown]
Additionally, TEAEs by sex, TEAEs by age group I, serious TEAEs and TEAEs by intensity (mild/moderate/severe/unknown) will be tabulated. Related TEAEs (defined as possibly, probably, or definitely related, or with missing relationship) will be presented by intensity overall (related to IMP or related to medical device), related to IMP only, related to IMP and medical device and related to medical device only. Additionally, TEAEs by relationship (unrelated / unlikely related / probably related / probably related / definitely related) will be presented related to IMP and related to medical device separately.

TEAEs leading to death and TEAEs resulting in discontinuation of study will be tabulated if more than 5 events are observed. Specification of any action taken documented on AE page as 'Withdrawal from study' will be used for detection of TEAEs resulting in discontinuation of study.

A listing of subjects with TEAEs will be provided for all TEAEs reported. Non-TEAEs, i.e. AEs with onset before treatment or later than 4 weeks after each PDT cycle, will be listed separately for all subjects enrolled. In listings, the start day of the AE relative to start of treatment will be calculated for complete start dates only. Duration of events is only calculated for complete start and end dates.

